5.3 Univariate and multivariate Analyses

Univariate and multivariate Cox regression analyses will be used to assess the effect of baseline and post-procedural covariates on the primary effectiveness endpoint and primary safety endpoint. These analyses will be performed as ancillary to the primary endpoint analyses.

A univariate analysis will model the effect of each covariate within each treatment group. A multivariate analysis will model the time to ischemic stroke or SE on each covariate as well as treatment and covariate-by-treatment interaction. The covariates to be included in these modelling analyses are as follows:

- CHA₂DS₂-VASc score at baseline
- HAS-BLED score at baseline
- Concomitant vs sequential ablation
- Device size

For all of the modelling analyses mentioned in this section, continuous or ordinal measures may be dichotomized (e.g. age \geq 75, LVEF <40, device size \leq 24).

5.4 Pooling Analyses

The analyses of the primary effectiveness and safety endpoints will be presented using data pooled across investigational centers and geographic regions. Analyses will be performed to justify this pooling. Poolability will be assessed across site, geographical region, and sequential vs. concomitant ablation for each primary endpoint. Results will also be presented separately for site, geographical region, and sequential vs. concomitant ablations regardless of the results of the poolability assessments. Sites that successfully implanted with 5 subjects or fewer will be considered "small sites" and will be grouped together as one site per geographical region for the purpose of poolability assessment.

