8.1. Scale and Duration

A maximum of 1600 subjects will be randomized in the study at a maximum of 150 global sites. A maximum of 260 additional patients will be treated in the roll-in phase of the study.

The duration of the study is expected to last approximately 64 months. The duration of individual subject participation is expected to last approximately 36 months but may vary per subject.

Given the number of sites that have PINNACLE FLX experience, and the total number of planned sites, it is expected that the number of roll-ins in the United States will be approximately 130.

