11.6. Randomization

Randomization will occur after all clinical and transthoracic echo criteria have been verified and the baseline assessment is complete. Randomization will occur no later than 30 days following consent. Subjects will be randomized 1:1 (Device: Control) and randomization will be stratified by sequential vs. concomitant planned ablation to help ensure balance of treatment assignments within the sequential and concomitant groups.

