13.2.3. Number of Subjects per Investigative Site

To avoid any site effect and bias, no site will be authorized to implant or attempt more than 15% of the 1600 randomized subjects (n = 240) per this protocol without prior approval from the sponsor.

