1 PROTOCOL SYNOPSIS

Comparison	Comparison of An ti coagulation with Left Atrial Appendage Closure after AF Ablatio n (OPTION)						
Study Objective(s)	The primary objective of this study is to determine if left atrial appendage closure with the WATCHMAN FLX Device is a reasonable alternative to oral anticoagulation following percutaneous catheter ablation for high risk patients with non-valvular atrial fibrillation.						
Planned Indication(s) for Use	The planned indication for use within the OPTION study is as follows: The WATCHMAN and WATCHMAN FLX Device are indicated to reduce the risk of thromboembolism from the left atrial appendage in subjects with non-valvular atrial fibrillation who: • Are at increased risk for stroke and systemic embolism based on CHA2DS2-VASc scores following catheter ablation of atrial fibrillation; and • Are deemed to be suitable for anticoagulation therapy Note: In countries where CE mark applies, the OPTION indication is within the CE mark approved Indication for Use.						
Study Design	This study is a prospective, randomized, multi-center, global investigation to determine if left atrial appendage closure with the WATCHMAN FLX Device is a reasonable alternative to oral anticoagulation in patients after AF ablation.						
Planned Number of Subjects	A maximum of 1600 subjects will be randomized in the study. Note the total number of enrolled patients is expected to exceed the number of randomized subjects since sites without WATCHMAN FLX experience are required to perform two roll-in cases. A maximum of 260 patients will be treated in the roll-in phase of the study, including approximately 130 roll-in subjects in the United States. The roll-in cohort will be analyzed separately from the primary cohort of randomized subjects.						
Planned Number of Centers / Countries	Up to 150 investigational centers worldwide						
Primary Effectiveness Endpoint	WATCHMAN therapy is non-inferior for the occurrence of stroke (including ischemic and/or hemorrhagic), all cause death, and systemic embolism at 36 months.						

Comparison of Anticoagulation with Left Atrial Appendage Closure after AF Ablation (OPTION)						
Primary Safety Endpoint WATCHMAN therapy is superior for non-procedural bleeding throu months (ISTH major bleeding and clinically relevant non-major blee						
Secondary Endpoint	WATCHMAN therapy is non-inferior for ISTH major bleeding at 36 months (including procedural bleeding)					

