5.4.1 Pooling of Investigational Centers

Center-to-center heterogeneity will be assessed for the primary effectiveness and safety endpoint using a shared frailty model. Time-to-event endpoint will be modelled on randomized treatment group, with investigational center included as a random effect with a lognormal distribution. Centers will be deemed heterogeneous with respect to the primary effectiveness and safety endpoint if the p-value from Wald test for the investigational center random effect is <0.15.

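### Merging all sites with five or fewer implants before the centre frailty test makes the plan's only formal check of between-site differences less sensitive

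*SAP*

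**What the plan says.** SAP 5.4 sets out analyses meant to justify pooling across centres and regions. Its grouping rule reads "Sites that successfully implanted with 5 subjects or fewer will be considered" small, and these sites "will be grouped together as one site per geographical region for the purpose of poolability assessment". Protocol 13.3.4 has the same rule. The count is of successful implants. Control subjects do not enter it, nor do Device subjects whose implant was not attempted or failed.

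The formal centre test is in SAP 5.4.1 (Protocol 13.3.4.1). It is a shared frailty model on randomized treatment, with "investigational center included as a random effect with a lognormal distribution". Centres are declared heterogeneous if the Wald p-value for that effect is below 0.15.

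Two other statements bear on the point. SAP 5.4 adds: "Results will also be presented separately for site, geographical region, and sequential vs. concomitant ablations regardless of the results of the poolability assessments". On scale, Protocol 8.1 says: "A maximum of 1600 subjects will be randomized in the study at a maximum of 150 global sites". The SAP synopsis likewise gives "Up to 150 investigational centers worldwide". Neither document gives an expected distribution of site sizes or the number of regions.

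**The concern.** The cut of five implants lies almost exactly at the average Device enrolment per site if the trial uses its full allowance of sites. A rule intended for unusually small centres would then catch the typical one. Once such sites are merged by region, the differences among them are averaged out before the frailty model sees them, and the model has fewer clusters from which to estimate a variance.

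The criterion is also lopsided. It depends on something that happens after randomization, in one arm only, so a site with about ten randomized subjects can be small.

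At stake is what a non-significant centre test can be taken to mean. The test is offered as support for pooling. If the grouping rule lowers its chance of finding real differences, a finding of poolable is weaker evidence than it appears.

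**Working it through.** **Inputs from the documents.** At most 1600 randomized subjects and 150 sites (Protocol 8.1); 1:1 allocation (Protocol 11.6); small-site cut of 5 implants (SAP 5.4); Wald threshold 0.15 (SAP 5.4.1); 10% event rate and 15% attrition at 36 months (SAP 3.1.2).

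**Assumptions.** Shape of the site-size distribution, three regions, site log-SDs of 0.4 and 0.6, and every Device subject implanted unless stated.

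**Step 1: the plan's own figure.** The documents state no number of small sites. The figure that drives the arithmetic is N. Farrington-Manning power with 680 per arm, 10% in both arms, margin 5% and one-sided alpha 0.025 is 85.88%, against 85.9% stated. Attrition: 1360/(1 - 0.15) = 1600. Both reproduce.

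**Step 2: mean site size.** Device subjects: 1600/2 = 800. At 150 sites: 800/150 = 5.33 Device and 1600/150 = 10.67 randomized subjects per site.

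**Step 3: expected share of small sites.** If sites recruit at equal rates, implants per site are Poisson and the share is P(X ≤ 5) = e^(-m) Σ m^x/x!, x = 0 to 5, with m = 800/sites. Uneven recruitment is represented by a negative binomial with the same mean and k from 4 to 0.7.

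| Sites | Mean implants | Poisson | Negative binomial, k = 4 to 0.7 | Device subjects in small sites |
|---|---|---|---|---|
| 150 | 5.33 | 56% | 59-67% | 21-38% |
| 130 | 6.15 | 42% | 50-63% | 18-27% |
| 100 | 8.00 | 19% | 35-55% | 10-15% |

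Checks at 150 sites:
- An exactly even split gives 100 sites with 5 implants and 50 with 6 (100 × 5 + 50 × 6 = 800), so 67% are small.
- The arithmetic floor is 11%: at most 133 sites can reach 6 implants (800/6 = 133.3), which leaves 17 of 150.
- With 98.5% implant success (the registry figure in Protocol 4.2) the range is 57-67%; with 90% it is 65-70%.

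**Step 4: effect on the centre test.** Simulation with 150 sites, 1600 subjects, exponential event and attrition times, a lognormal site effect, no treatment effect, three regions and Wald p < 0.15. The model was fitted to the same data unmerged and merged, with 150 runs per setting (Monte Carlo error about 4 points). The 17% rate is the midpoint of the 14% and 20% assumed for the safety endpoint in SAP 3.2.2.

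| Event rate | Site log-SD | Near-equal sites: unmerged → merged | Uneven sites: unmerged → merged |
|---|---|---|---|
| 10% | 0.4 | 27% → 6% | 38% → 20% |
| 10% | 0.6 | 79% → 36% | 88% → 55% |
| 17% | 0.4 | 61% → 25% | 62% → 37% |
| 17% | 0.6 | 100% → 71% | 99% → 92% |

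Merging left about 69 analysis units with near-equal sites and about 60 with uneven sites. With no site effect and a 10% event rate, the unmerged test rejected in 3-5% of runs, so its advantage is not bought with false positives.

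A separate simulation of the same test at the 10% rate gave 27-41% falling to 6-15% for SD 0.4, and 89-93% falling to 41-71% for SD 0.6. Taking both together, the ranges are 27-41% to 6-20%, and 79-93% to 36-71%.

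**The case against.** The strongest reply has five parts.

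- **150 sites is a maximum.** A reader might infer that over half of the sites will be merged. The documents do not support that as a fact: they give a ceiling and no distribution, and at 100 sites the share could be as low as 19%. This stands.
- **By-site results appear whatever the test says.** A reader might infer that the rule hides heterogeneity. It does not: the merge applies only to the poolability assessment, region is assessed separately and larger sites remain their own clusters. This stands, but it does not restore the test. At about 10.67 × 0.10 = 1.07 efficacy events per site, a by-site table cannot show between-site variation by eye, and a regional comparison cannot see variation within regions.
- **Nothing confirmatory depends on the result.** A reader might infer a threat to the primary conclusions. The frailty model has no centre-by-treatment term, so it addresses differences in baseline risk, and neither the primary tests (SAP 3.1.3, 3.2.3) nor the success rule (SAP 3.3.5) refers to it. This stands in full.
- **The unmerged test is itself weak.** At SD 0.4 and a 10% event rate it detects only 27-41%. That is true, but it argues against discarding more information. The unmerged model could be fitted with about one event per site.
- **Counting successful implants matters little numerically.** At 98.5% success the Poisson share moves only from 56% to 57%. This stands; leaving out Controls is the larger flaw in the definition.

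The rule also does not say whether roll-in implants count. Because the synopsis has the roll-in cohort analysed separately, the natural reading is that they do not. If two counted at 130 of 150 sites (an assumption), the Poisson share would fall to about 27%.

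**Conclusion.** The concern holds as a loss of sensitivity in one supporting analysis. At the 150-site ceiling the rule would be expected to merge more than half of the sites under every recruitment pattern tried. With fewer sites, the share depends on how uneven recruitment is. Merging lowered detection in every setting simulated, at the 10% event rate usually to about half of the unmerged figure or less. The size of the loss rests on the assumed site distribution, three regions and the chosen site SDs; the direction was the same throughout.

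The consequence is limited to the weight that a non-significant centre test can carry as justification for pooling. The primary estimates, hypothesis tests and success criteria are untouched. This is a cheap improvement and not a defect in the confirmatory analysis.

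**What to change.** 1. In SAP 5.4 and 5.4.1, fit the shared frailty model with every site as its own cluster. At minimum, prespecify that fit and report it alongside the merged one.
2. Where by-site grouping is still needed, define a small site by total subjects randomized in both arms, and state that roll-in subjects are excluded.
3. Make the same edit in Protocol 13.3.4.

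The cost is one more model fit and a wording change in both documents. No new data, sample-size change or change to the primary analyses is needed. Protocol 13.3.10 already provides for changes made before the analyses through an amended SAP.

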5.4.1 Pooling of Investigational Centers

Center-to-center heterogeneity will be assessed for the primary effectiveness and safety endpoint using a shared frailty model. Time-to-event endpoint will be modelled on randomized treatment group, with investigational center included as a random effect with a lognormal distribution. Centers will be deemed heterogeneous with respect to the primary effectiveness and safety endpoint if the p-value from Wald test for the investigational center random effect is <0.15.

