13.3.4.1. Pooling of Investigational Centers

Center-to-center heterogeneity will be assessed for the Primary and Secondary endpoints using a shared frailty model. Time to event variables will be modelled on randomized treatment group, with investigational center included as a random effect with a lognormal distribution. Centers will be deemed heterogeneous with respect to the Primary Effectiveness Endpoint if the p-value from Wald test for the investigational center random effect is <0.15.

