5.2 Subgroup Analyses

Primary effectiveness and safety endpoint results will be summarized. Additionally, treatment groups compared based on the following subgroups:

- Sequential vs Concomitant patients
- Male vs female
- Age at time of consent (< 75 years vs. ≥ 75 years)
- Stroke risk (CHA₂DS₂-VASc score 2-3, 4-5, and >5)
- Bleeding risk (HAS-BLED scores of 0, 1-2, and > 2)
- AF type at baseline (paroxysmal, persistent, permanent)
- Implanting image techniques (TEE vs CT for core lab data)

Time-to-event curves will be constructed for each treatment group, HRs and log-rank test p-values will be calculated within each subgroup, and subgroup by treatment interactions will be tested using Cox regression.

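### The center poolability test detects differences in overall center risk and cannot separate them from differences in treatment effect

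*SAP*

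**What the plan says.** SAP 5.4 presents the two primary endpoints pooled over centers and regions and states: "Analyses will be performed to justify this pooling". It names three factors to be assessed: site, region, and sequential versus concomitant ablation.

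The only method given is for centers, in SAP 5.4.1: a shared frailty model for each endpoint with treatment arm as the one covariate, "with investigational center included as a random effect with a lognormal distribution". Centers are declared heterogeneous if the "p-value from Wald test for the investigational center random effect is <0.15". Protocol 13.3.4.1 has the same model: "Time to event variables will be modelled on randomized treatment group, with investigational center included as a random effect with a lognormal distribution". Neither document includes a treatment-by-center or treatment-by-region term. No method or threshold is given for region, and no consequence follows from a finding of heterogeneity.

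Three neighbouring provisions matter:

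- SAP 5.4: "Results will also be presented separately for site, geographical region, and sequential vs. concomitant ablations regardless of the results of the poolability assessments". This is presentation only, with no test attached.
- SAP 5.2: "subgroup by treatment interactions will be tested using Cox regression". The listed subgroups include sequential versus concomitant, but not center or region. The covariate-by-treatment models in SAP 5.3 do not list center or region either.
- The small-site rule in SAP 5.4: "Sites that successfully implanted with 5 subjects or fewer will be considered" small and merged within region.

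**The concern.** Pooling a randomized comparison rests mainly on the treatment effect being reasonably consistent across the units pooled. The planned model assumes that consistency, because it has a single treatment coefficient, and then tests something else: whether centers differ in event rate across both arms together. A flag may reflect only differing patient mix. A pass may coexist with a device effect that varies by center. In a device trial that requires roll-in cases at inexperienced sites (Protocol 8) and caps site volume to limit site effects (Protocol 13.2.3), variation in the device effect is what a reader would expect this section to address.

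The small-site rule adds a lesser problem. It groups sites by a count that arises after randomization and in effect only in the Device arm. Number randomized would not have that dependence.

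At stake is what the poolability statement in the report can support, not the primary tests themselves.

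**Working it through.** **1. The plan's own figure.** The documents give no operating characteristics for the p<0.15 rule. The background design figure does reproduce. Farrington-Manning with 680 per arm, 10% in both arms, margin 5 points and one-sided 0.025 has restricted estimates of 13.03% and 8.03%. The null standard error is √[(0.1303×0.8697 + 0.0803×0.9197)/680] = 0.01659, and the alternative standard error is √[2×0.10×0.90/680] = 0.01627. Power = Φ[(0.05 − 1.96×0.01659)/0.01627] = Φ(1.07) = 85.9%, as stated in SAP 3.1.2. Also 1360/0.85 = 1600.

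**2. What the model tests.** For subject i in center j with treatment indicator x, the hazard is λ₀(t)·exp(β·x_ij + b_j), with b_j ~ N(0, τ²). The term b_j multiplies the hazard in both arms and β is the same everywhere. The rule tests τ² = 0, which is no variation in overall center risk. A test of effect consistency needs a further term, such as x_ij·c_j with its own variance, or treatment by region.

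**3. Simulation.** From the documents: 1600 subjects, 1:1 allocation, 10% efficacy event rate, and 17% as the mean of the safety rates (14% and 20%). Assumed: 50 or 100 unequal center units after merging, constant hazards, 2.65 years' mean follow-up, average hazard ratio 1, and the heterogeneity SDs shown. Each of the four combinations of unit count and event rate had 300 trials per scenario, so the Monte Carlo standard error is at most 2.9 points (√[0.25/300]). A one-sided Wald test on the variance stands in for the SAS test. Entries are the share of trials with p<0.15, ranged over the four combinations.

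| Truth (log-hazard scale) | Planned center test | Treatment-by-center test |
|---|---|---|
| No heterogeneity | 6–12% | 6–12% |
| Baseline risk SD 0.5, same effect everywhere | 91–99% | 10–16% |
| Effect SD 0.5, average center log-hazard unchanged | 8–13% | 32–58% |
| Effect SD 1.0, average center log-hazard unchanged | 20–31% | 91–100% |
| Effect SD 1.0, Device arm only | 99–100% | 98–100% |

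Row 2 shows flags with no difference in effect. Row 3 shows moderate effect variation that the planned test barely registers. In row 5 the variation also shifts each center's total event rate, so the planned test responds, but it cannot say which cause is at work.

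**4. Information per center.** At the 150-center ceiling, 1600/150 = 10.7 randomized subjects per center. That is about 5.3 in the Device arm and, at 10%, about 1.1 efficacy events. The average center therefore sits at the five-implant cutoff, where a failed implant can decide how a site is grouped. The treatment-by-center test has low power here: at a 10% event rate and SD 0.5, 32–37% by the Wald test and 31–43% by a boundary-corrected likelihood-ratio test.

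**The case against.** The strongest reply has four parts.

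- **The test does respond to some effect variation.** If implant performance drives the variation, it would plausibly appear in the Device arm only, and row 5 shows almost certain detection at SD 1.0. In a cruder dispersion calculation (100 equal sites of 16), the center-risk test flagged treatment-only heterogeneity more often than an interaction test did, 57% against 40%. This stands. A reader might infer that the planned test is blind to varying device effects. It is not; it is non-specific, and what it detects depends on the mechanism.
- **Center risk is a proper question in this trial.** A reader might infer that baseline differences are irrelevant under randomization. The efficacy test compares an absolute difference with a fixed 5-point margin, so risk level matters even with a constant hazard ratio. With an assumed hazard ratio of 1.3, control risk of 5% gives 1 − 0.95^1.3 = 6.45%, a difference of 1.45 points. Control risk of 20% gives 1 − 0.80^1.3 = 25.18%, a difference of 5.18 points, beyond the margin. This stands and is why the frailty model should stay.
- **Part of the gap is covered.** Sequential versus concomitant has an interaction test, and site and region results are displayed whatever the tests show. This stands for ablation timing. For center and region, a display without a test or criterion is only a partial answer.
- **No decision depends on the result, and a center-level interaction test is weak.** Both are true. They limit the importance of the point and favour a region-level test, but they do not make the planned test answer the pooling question.

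**Conclusion.** The point holds as a limited one. The planned rule detects center differences in overall risk and cannot separate these from differences in treatment effect. Neither outcome of the rule, taken alone, shows whether pooling the comparison across centers or regions is justified.

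The structural conclusion follows from the model as written. The sizes rest on assumed center counts, center sizes and heterogeneity SDs, and on a stand-in for the SAS Wald test. The 91–99% figure illustrates behaviour at SD 0.5 and does not predict this trial's result.

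A reader might go further and infer that pooling is invalid or that the primary conclusions are at risk. The documents do not support that. The primary analyses are a Kaplan-Meier difference and a log-rank test, neither uses the frailty model, and type I error and sample size do not change. Nothing shows that the small-site rule would alter any result; it is a minor correction to make at the same time.

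**What to change.** In SAP 5.4 and 5.4.1, with matching wording in Protocol 13.3.4:

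1. Keep the shared frailty model, described as an assessment of between-center variation in overall risk and its relevance to the absolute margin.
2. Make a treatment-by-region (or treatment-by-pooled-site) interaction the main poolability test, at the 0.15 level, for each primary endpoint.
3. Add a random treatment-by-center term as supporting evidence, tested by a likelihood-ratio test with the boundary correction for a variance (half the one-degree-of-freedom chi-square tail).
4. State what follows from a flag, for example how the by-region results will be reported and interpreted.
5. Define small sites by number randomized; the cutoff should be set to suit that count.

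The cost is SAP wording and a few model terms, with no new data. The drawback is low center-level power, about 32–37% at SD 0.5 and a 10% event rate. A non-significant center-level result should therefore not be read as proof of consistency, and the region or pooled-site test should lead.
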